### 9.3 Analysis Sets

For the purposes of analysis, the following analysis sets are defined:

Participant Analysis Set	Description
Randomized	All participants randomized by study IRT to one of the 3 study doses (one of three study groups).
Safety Analysis Set (SafAS)	Participants who have received at least one study intervention. All participants will have their safety analyzed after each dose according to the intervention actually received, and after any dose according to the intervention received at the 1st dose. Safety data recorded for a vaccine received out of the protocol design will be excluded from the analysis (and listed separately).
Full analysis set (FAS)	Subset of randomized participants who received at least 1 dose of the study vaccine and had a post-vaccination blood sample for D22 or D43.

	
Participants will be analyzed according to the study dose group to which they were randomized.

Per-protocol analysis set (PPAS)	
To be able to compare and present the results of immunogenicity in the same table, only one PPAS will be derived in this study.
 
Subset of the FAS participants who have provided D22 and D43 blood samples. Participants presenting with at least one of the following relevant protocol conditions will be excluded from the PPAS:
 

• Participant did not meet all protocol-specified inclusion criteria or met at least one of the protocol-specified exclusion criteria

• Participant did not complete the vaccination schedule

• Participant received a vaccine other than the one that he / she was randomized to receive

• Preparation and / or administration of vaccine was not done as per-protocol

• Participant did not receive vaccine in the proper time window

• Participant did not provide a post-dose serology sample at D22 (+7 days) and D43 (+7 days) in the proper time window or a post-dose serology sample was not drawn

• Participant received a medication impacting or that may have an impact on the immune response as described in Section 6.8

• Re-randomized participants

 
Any other deviation identified during the study conduct and judged by the clinical team during data review as having a potential impact on the assessment of immunogenicity will be used to exclude a participant from the PPAS.
 
Participants with missing SN data or participants with no valid test results of SN will be included in PPAS if they meet all the other requirements to be included in PPAS for HIH.
 
In the event of a local or national immunization program with a SARS-CoV-2 or other vaccine, participants who receive 1 or more doses of the vaccine listed above at any time during the study will not be withdrawn from the study.

## 9.4 Statistical Analyses

The SAP core body will be finalized before the initiation of the study and may be amended, if necessary, prior to database lock. It will include a more technical and detailed description of the statistical analysis outlined in this section.

### 9.4.1 General Considerations

The statistical analysis will be conducted as follows:

- The study will be unblinded after all immunogenicity and safety data are collected for the follow-up period of 3 weeks after D22 (ie, 21 days after the last vaccination) (see [Section 6.3.2](#) and [Section 9.5](#)).
- The final database lock will occur after the 12-month follow-up.

No adjustment for multiplicity regarding multiple comparisons between study doses is planned in this study. Details will be provided in the SAP.

#### 9.4.2 Primary Endpoints

##### Primary Immunogenicity Objective:

The immunogenicity parameters will be calculated with their 95% CIs using the exact binomial distribution (Clopper-Pearson method) for proportions and using normal approximation of log-transformed for GMTs and GMTs ratio. The 95% CI of proportions difference (ie, difference between vaccine groups in seroconversion) will be calculated using Wilson Score method without continuity correction ([19](#)). All analyses will be conducted by study group and also by age stratum.

The time windows used for collecting blood samples are: D01, D22 [+7], D43 [+7], D202 [+14], and D387 [+14]. To avoid redundancy and typing errors, these time windows will not be reported in all sections of this document.

- Immunogenicity by HIH measurement method
  - GMTs of HAI Ab titers obtained on D22, and on D43 for comparison with D01, D202, and D387.
  - Geometric mean of individual ratios of HAI Ab titers D22/D01 and D43/D01; and D202/D01 and D387/D01.
  - Percent of participants with seroconversion defined as HAI Ab titer < 10 (1/dilution [1/dil]) on D01 and post-injection titer  $\geq$  40 (1/dil) on D22 or D43; or defined as HAI Ab titer  $\geq$  10 (1/dil) on D01 and a  $\geq$  4-fold increase in titer (1/dil) on D22 or D43.  
The interpretation of the results will account for seroconversion thresholds reported in FDA guideline ([18](#)) for participants 18 – 64 years and  $\geq$  65 years of age.
  - Percent of participants with HAI Ab titers  $\geq$  40 (1/dil) on D22, and percent of participants with HAI Ab titers  $\geq$  40 (1/dil) on D43. The same statistic will be calculated for D01, D202, and D387.  
The interpretation of the results will account for seroconversion thresholds reported in FDA guideline ([18](#)) for participants 18 – 64 years and  $\geq$  65 years of age.
  - Percent of participants with detectable HAI Ab titer with a titer  $\geq$  10 (1/dil) on D01, D22, D43, D202, and D387.
  - Difference and its 95% CI in seroconversion between the 3 study doses (Group 1 - Group 3; Group 2 - Group 3, and Group 2 - Group 1) at D22 and D43.
  - Ratio of GMTs and its 95% CI for: Group1/Group3, Group2/Group3, and Group2/Group1 at D22, and at D43.

- The RCDCs of pre-vaccination titer prior to the first vaccination (D01), and post-vaccination titer at D22, D43, D202, and D387 will be generated for each study dose. The RCDCs will include the plots of the 3 doses on the same figure.
- Immunogenicity by SN measurement method
  - GMTs of NT Ab titer obtained on D22, and on D43 for comparison with D01, D202, and D387.
  - Geometric mean of individual ratios of NT Ab titer for D22/D01, D43/D01, D202/D01, and D387/D01.
  - Percentage of participants with NT Ab titers  $\geq 20$  (1/dil),  $\geq 40$  (1/dil),  $\geq 80$  (1/dil) on D22, and on D43; compared to D01, D202, and D387.
  - Percent of participants with fold increase in NT Ab titer [post-vaccination/ pre-vaccination]  $\geq 2$  and  $\geq 4$  on D22 and D43.
  - Percent of participants with detectable NT Ab titer  $\geq 10$  (1/dil) on D01, D22, D43, D202, and D387.
  - Difference and its 95% CI in percent of participants with fold increase between the 3 study doses (Group 1 - Group 3, Group 2 - Group 3, and Group 2 - Group 1) on D22, and on D43.
  - Ratio of GMs and its 95% CI for: Group1/Group3, Group2/Group3, and Group2/Group1 on D22, and on D43.
  - The RCDCs of pre-vaccination titer prior to the first vaccination (D01) and post-vaccination titer at D22, D43, D202, and D387 will be generated for each study dose. The RCDCs will include the plots of the three doses on the same figure.

For each immunogenicity measurement method, the analysis will be conducted for each immunogenicity variable on the PPAS and on FAS.

#### 9.4.3 Secondary Endpoints

##### Safety Objective:

For the main safety parameters, 95% CIs of point estimates will be calculated using exact binomial method (Clopper-Pearson method) for single proportions and using the normal approximation for quantitative data.

All analyses will be descriptive; no hypotheses will be tested.

The number of participants with documented safety will be used as denominator of the frequencies.

- For solicited reactions, the denominator will be the total number of participants who have non-missing data for the endpoint considered
- For unsolicited AEs, the denominator will be the total number of participants who were vaccinated with the dose analyzed

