**Protocol Title:**

A parallel-group, Phase I/II, randomized, modified double-blind, 3-arm, active comparator, multi-center, prevention study to evaluate the immunogenicity and safety of two adjuvanted dose levels of Panblok H7+MF59 influenza vaccine compared with an unadjuvanted dose of Panblok H7 in participants 18 years of age and older

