**Brief Title:**

Study on Two Adjuvanted Dose Levels of Panblok H7+MF59 Compared for Immunogenicity and Safety with an Unadjuvanted Dose of Panblok H7 in Participants 18 Years of Age and Older

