**Rationale:**

VAM00001 will be a Phase I/II, randomized, modified double-blind, multi-center, prevention study to be conducted in approximately 700 adult participants (350 adults 18 - 64 years of age and 350 adults  $\geq$  65 years of age). The aim of this study is to assess the immunogenicity and safety of 2 dose levels of Panblok H7+MF59 (7.5  $\mu$ g and 15  $\mu$ g of recombinant hemagglutinin [rHA]) compared with an unadjuvanted dose of Panblok H7 (45  $\mu$ g of rHA) in order to select one dose formulation for further clinical development. An active unadjuvanted comparator was chosen to potentially assess an antigen-sparing effect of the MF59 adjuvant. Participants will be randomized in a 3:3:1 ratio and the vaccination schedule for all participants will consist of 2 doses, administered 21 days apart.

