**Secondary endpoints (Safety):**

For the main safety parameters, 95% CIs of point estimates will be calculated using exact binomial method (Clopper-Pearson method) for single proportions and using the normal approximation for quantitative data.

Analysis will be conducted for each dose group, by strata of age, and by the period of 7 days and / or the period of 21 days after each vaccination, and / or by interval of visits (ie, between Visit 4 [6-month follow-up] and Visit 5 [12-month follow-up]) for safety data collected from D01 to the end of the study.

All analyses will be descriptive, and no hypotheses will be tested.

The number of participants with documented safety will be used as denominator of the frequencies.

[figure not shown]

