
Safety
 
To assess the safety profile in each study vaccine group in participants 18 - 64 years and <math>\geq</math> 65 years of age throughout the study
	
Safety
 
The following safety endpoints will be described:
 

• Presence of any unsolicited systemic AEs reported in the 30 minutes after each vaccination

• Presence of solicited (prelisted in the participant's eDiary and CRB) injection site reactions and systemic reactions occurring up to 7 days after each / any vaccination

• Presence of unsolicited AEs up to 21 days after each / any vaccination

• Presence of MAAEs throughout the study

• Presence of AESIs throughout the study

• Presence of SAEs (including AESIs) throughout the study

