### 3.4.3 Secondary Endpoints

#### Safety

For the main safety parameters, 95% CIs of point estimates will be calculated using exact binomial method (Clopper-Pearson method) for single proportions and using the normal approximation for quantitative data.

All analyses will be descriptive; no hypotheses will be tested.

The number of participants with documented safety will be used as denominator of the frequencies:

- For solicited reactions, the denominator will be the total number of participants who have non-missing data for the endpoint considered.
- For unsolicited AEs, the denominator will be the total number of participants who were vaccinated with the dose analyzed.

In terms of contents, solicited reactions will be presented by time to onset, maximum severity, number of days of occurrence and action taken; unsolicited AEs will be presented by causal relationship, time of onset, maximum severity, and duration; SAEs will be presented by causal relationship, seriousness, and outcome.

Subgroup analysis will also be performed; in particular, the main safety endpoints will be summarized according to age subgroups, sex, and race, as appropriate according to number of participants in the respective subgroups.

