### 3.5 Interim Analysis

The blind will be broken at the participant level after collecting all immunogenicity and safety data up to 21 days after last vaccination, data are cleaned, and database is locked. The study participants and the laboratory personnel who analyze the blood samples will remain blinded throughout the study. The study team will strive not to communicate the study unblinded data to the sites until the interim CSR sign-off, to minimize the bias in collecting the follow-up safety data.

The main analysis of immunogenicity (HIH and SN measurement methods) data and safety will include all data up to 21 days after the last vaccination. The results of this analysis will help in selecting the dose formulation for further clinical development. The results of this main analysis may be reported in an interim clinical study report (CSR).

HIH and/or SN results will be evaluated, discussed, and used in selecting the best Panblok formulation with the most suitable immunogenicity response and safety for further clinical development.

A final database lock will occur after all data, including up to the 12-month follow-up period, are collected. A final CSR would include the analysis of the safety and immunogenicity data at 6- and 12-month after the last vaccination to assess the persistence of the antibody levels.

No hypothesis will be tested, thus adjustment for multiplicity is not necessary.

Unblinded early looks at the safety data may take place to assess safety.

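### Titles, aim and dose selection treat safety as comparative, but no between-group safety difference with a confidence interval is pre-specified

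*Protocol*

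**What the plan says.** **Purpose.** The protocol title sets out "to evaluate the immunogenicity and safety of two adjuvanted dose levels of Panblok H7+MF59 influenza vaccine compared with an unadjuvanted dose of Panblok H7". The brief title has "Two Adjuvanted Dose Levels of Panblok H7+MF59 Compared for Immunogenicity and Safety with an Unadjuvanted Dose of Panblok H7". The Rationale opens its aim with "The aim of this study is to assess the immunogenicity and safety of 2 dose levels of Panblok H7+MF59", goes on to name the unadjuvanted 45 µg vaccine as comparator, and gives selection of one formulation as the reason.

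**Decision.** Under SAP 3.5, the HIH and/or SN results from the main analysis are to be "used in selecting the best Panblok formulation with the most suitable immunogenicity response and safety for further clinical development".

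**Formal safety objective.** Protocol Table 3.1 is narrower: "To assess the safety profile in each study vaccine group in participants 18 - 64 years and" 65 and over. It names no comparator. SAP Table 2.1 matches it.

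**Safety analysis.** Protocol 9.4.3: "95% CIs of point estimates will be calculated using exact binomial method (Clopper-Pearson method) for single proportions". SAP 3.4.3 repeats the method: "exact binomial method (Clopper-Pearson method) for single proportions and using the normal approximation for quantitative data". The protocol synopsis gives the unit of analysis: "Analysis will be conducted for each dose group, by strata of age". The other planned safety summaries (event counts, time to onset, days of occurrence, intensity, relationship) are also within group.

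**Immunogenicity analysis.** Protocol 9.4.2 and SAP 3.4.2 plan Group 1 − Group 3, Group 2 − Group 3 and Group 2 − Group 1 differences in HAI seroconversion and in NT fold increase, each with a 95% CI, plus the corresponding ratios of geometric means. Differences of proportions use the Wilson-score method without continuity correction.

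**The concern.** Two inputs feed the choice of formulation, and the plan handles them differently. For immunogenicity, the randomised contrast is estimated with its uncertainty. For safety, the reader gets one percentage per group with its own interval and must make the comparison unaided.

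The contrasts that matter are the added reactogenicity of each adjuvanted dose over unadjuvanted vaccine (Groups 1 and 2 against Group 3) and of the higher over the lower adjuvanted dose (Group 2 against Group 1). The protocol's background makes the first a live question. Three earlier Panblok studies, with other adjuvants, saw more injection-site pain and tenderness with adjuvanted than with unadjuvanted vaccine. The earlier MF59 study, as summarised there, had no unadjuvanted arm and enrolled adults aged 18 to under 50.

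If no contrast is fixed beforehand, someone comparing two separate intervals may see overlap and conclude that there is no difference. Alternatively, safety contrasts may be picked after the D43 unblinding.

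**Working it through.** **1. The plan's own figures.** The documents give no sample-size or precision figure for safety. Their figures for immunogenicity reproduce. Summing exact binomial probabilities over outcomes whose Clopper-Pearson lower limit exceeds the threshold gives, for protocol Table 9.2, 95.7, 87.7, 81.7, 92.6, 63.9 and 82.6% (titer ≥ 1:40) and 89.9, 79.1, 81.7, 80.2, 97.2 and 72.4% (seroconversion). All 12 rows agree with the stated values or with the < 80% entries. Also 630 / 0.9 = 700.

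**2. Inputs for the safety check.**
- Group sizes, from the planned numbers of participants: 150 / 150 / 50 per age stratum and 300 / 300 / 100 overall. All are assumed to contribute safety data.
- Reaction rates: **assumed**, because the background describes reactogenicity only qualitatively. A range is shown.

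**3. Worked example, one age stratum, 90/150 against 20/50.**

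Planned output, Clopper-Pearson:
- 90/150 = 60% (51.7 to 67.9)
- 20/50 = 40% (26.4 to 54.8)

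The intervals overlap between 51.7 and 54.8.

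Difference by the plan's Wilson-score method. With d = p1 − p2 and single-sample Wilson limits (l, u):

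lower = d − √[(p1 − l1)² + (u2 − p2)²]; upper = d + √[(u1 − p1)² + (p2 − l2)²]

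The Wilson limits are 0.520 to 0.675 for 90/150 and 0.276 to 0.538 for 20/50.
- lower = 0.20 − √(0.080² + 0.138²) = 0.20 − 0.160 = 0.040
- upper = 0.20 + √(0.075² + 0.124²) = 0.20 + 0.145 = 0.345

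The difference is +20 points (4.0 to 34.5), which excludes zero.

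**4. Precision over a range of assumed rates** (adjuvanted minus Group 3, in points, 95% CI).

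| Assumed rates | 300 vs 100 | 150 vs 50 |
|---|---|---|
| 30% vs 20% | +10 (−0.1 to 18.6) | +10 (−4.7 to 21.7) |
| 40% vs 20% | +20 (9.6 to 28.7) | +20 (5.0 to 31.9) |
| 60% vs 40% | +20 (8.7 to 30.5) | +20 (4.0 to 34.5) |
| 60% vs 30% | +30 (18.9 to 39.7) | +30 (14.1 to 43.2) |
| 10% vs 4% | +6 (−0.5 to 10.6) | +6 (−4.2 to 12.5) |

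**5. How often the two displays disagree.** Exact enumeration over all pairs of counts: the chance that the difference interval excludes zero, against the chance that the two Clopper-Pearson intervals do not overlap.

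| Assumed rates | Sizes | Difference excludes 0 | Intervals separate |
|---|---|---|---|
| 60% vs 40% | 150 vs 50 | 70.7% | 35.7% |
| 60% vs 40% | 300 vs 100 | 94.0% | 75.3% |
| 60% vs 30% | 150 vs 50 | 97% | 82% |
| 60% vs 30% | 300 vs 100 | 99.97% | 99.4% |
| 60% vs 50% (G2 vs G1) | 300 vs 300 | 70.4% | 35.6% |

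For an uncommon outcome, assumed 5% vs 2% at 150 vs 50, the difference interval excludes zero in only about 3% of trials. For a small dose effect, assumed 60% vs 55%, it does so in 15% (150 vs 150) or 24% (300 vs 300).

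**The case against.** **The analysis fits the objective as worded.** The safety objective is per group. The objective that names the unadjuvanted comparator is the immunogenicity one, and that one receives contrasts. This stands: a reader might infer that the plan fails its own safety objective, and it does not. It does not explain why an input to dose selection gets no contrast. Nor does the descriptive label, since the immunogenicity differences are descriptive too.

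**The difference can be derived.** A reader might infer that added reactogenicity gets no estimate at all. That goes too far. Counts and percentages per group are planned with defined denominators, so anyone can subtract them and compute an interval. What is missing is a pre-specified contrast and its interval.

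**Overlap is not a planned rule.** Correct. Step 5 shows how separate intervals may be misread; it does not describe a procedure in the plan. The rates are assumed, and the disagreement nearly vanishes when the true difference is large.

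**The contrast adds least where dose choice is hardest.** The earlier MF59 study reported no notable safety differences between dose levels. Small Group 2 − Group 1 differences and rare Grade 3 events would remain imprecise. This stands, but a wide interval states that imprecision openly.

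**Number of intervals.** Five endpoints × 3 contrasts × 3 populations × 3 periods (dose 1, dose 2, any dose) would be 135. This is a fair objection, and the reason for a shorter list.

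**Documents not supplied.** The SAP is to be read with its TLFs, and SAP 3.6 refers to a separate SAP for the safety management team. A contrast there cannot be excluded. Protocol section 9, however, makes the SAP core body the place where all the sponsor's analyses are described.

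**Conclusion.** The point holds in limited form. The titles, the aim and the decision input treat safety comparatively, while the pre-specified safety analysis is single-group. The supplied protocol and SAP fix no between-group safety difference with a confidence interval.

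The practical size depends on assumed rates. For common reactions the difference would have a half-width of roughly 9 to 11 points overall and 13 to 16 points per age stratum. For moderate differences such as 60% against 40%, separate intervals can overlap where the difference excludes zero. For large differences the two displays mostly agree, and for uncommon events neither is informative about a difference.

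This is a worthwhile, inexpensive improvement. It does not invalidate the planned safety summaries.

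**What to change.** Before the D43 unblinding, add to SAP 3.4.3 the risk differences Group 1 − Group 3, Group 2 − Group 3 and Group 2 − Group 1 with 95% CIs, by the Wilson-score method without continuity correction already specified for seroconversion. Present them overall and by age stratum, after any dose, for five endpoints:

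- any solicited injection-site reaction
- Grade 3 solicited injection-site reaction
- any solicited systemic reaction
- Grade 3 solicited systemic reaction
- any unsolicited AE within 21 days

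State that these are descriptive and unadjusted for multiplicity. If the TLFs already contain such contrasts, name them in the SAP core body.

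**Cost.** SAP wording and one or two tables, with no new data, participants or tests. The list gives 5 × 3 × 3 = 45 intervals. If every true difference were zero, about 45 × 0.05 ≈ 2 would be expected to exclude zero by chance, so no single interval should be read as a finding on its own.

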### ***Solicited reactions***

Solicited reactions will be presented according to their nature (Medical Dictionary for Regulatory Activities [MedDRA, the latest version at database lock] preferred term [PT]), intensity (Grade 1, 2, or 3), time to onset, and number of days of occurrence.

### ***Unsolicited AEs***

Unsolicited AEs included in the analysis will be summarized in the safety overview and analyzed according to their nature (MedDRA [the latest version at database lock] system organ class [SOC] and PT classification) and relationship to the vaccination.

### ***Injection Site Reactions***

For each dose, the number and percentage of participants experiencing any injection site reaction after injection will be calculated.

The description of injection site reactions will be presented according to:

- **Solicited injection site reactions**

All solicited injection site reactions that occur each day within 7 days after injection will be summarized and presented.

- **Unsolicited injection site reactions**

All unsolicited injection site reactions after vaccination, reported within 21 days after each vaccination will be described according to the type of events.

